9.3 Interim analyses and Stopping Rules

The objectives of interim monitoring are to 1) monitor for evidence of toxicity, 2) track participant accrual rates, 3) track study participant adherence to the prescribed medication, and to 4) monitor the primary outcome for early evidence of efficacy, harm or futility. To accomplish this, summaries of data quality, accrual, adherence, and distribution of baseline factors, toxicity, study endpoints and other analyses as requested will be prepared for review by the Data Safety Monitoring Committee (DSMB).

The primary outcome of the trial, changes in test scores between enrollment and the morning of surgery (baseline), Day 1 post CEA (12-25 h post-op) (eCD) and Day 30 +/- 5 days after CEA or Day of PO clinical visit (dCD), is the basis for formal interim analysis plan that follows.

One interim analysis and one final analysis are planned for ARM 2 of the trial, for a total of 2 analyses. These analyses will be performed when 0.66 and 1.0 fraction of the total number of participants in ARM 2 will have finished the approximately 30 day post-CEA assessment. Since ARM 2 will have a maximum sample size of 675 participants, we will have approximately 446 participants accrued and evaluated at approximately 30 days post-surgery at the time of the interim analysis.

We will use the Lan-DeMets approach, implementing an O'Brien-Fleming-type spending function that allots most of the type I error to the final look [Lan, K.K.G.; DeMets, D.L. Discrete sequential boundaries for clinical trials. *Biometrika* 1983, 70(3), 659-663]. The resulting alpha critical values to be used for each analysis are 0.0116 at the interim analysis, 0.05 at the final analysis.

The judgment by the DSMB and the NIA as to whether to continue the study will be based on the results of the interim analyses of the study's primary endpoint as well as other factors such as toxicity, adherence, secondary outcome measures, and development of any new external scientific evidence with regard to treatment with statins.

(The final study analysis of all arms (1-3) will be completed upon the conclusion of the study.)

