9.2 Sample Size and Randomization

Power Analysis

All of the aims will use logistic regression with presence of eCD as the response variable as the primary statistical analysis. A separate independent analysis for dCD will also be performed. Power calculations used data simulations (1000 simulations for each) with power=0.8, $\alpha=0.05$, and expected rates of eCD

based on existing preliminary data. For the comparison between subjects in arm 1 with a maximal dose (N=225) and those in arm 2 beginning with a sub-maximal dose and increasing to a maximal dose (N=338), the estimated minimum detectable effect size corresponds to a 65% reduction in eCD in the former cohort vs. the latter. For the comparison in between subjects in arm 2 beginning with a sub-maximal dose and increasing to a maximal dose (N=338) and those staying at the sub-maximal dose (N=337), the estimated minimum detectable effect size corresponds to a 46.7% reduction in eCD in the former cohort vs. the latter. For the comparison between subjects in arm 3 with 80 mg of atorvastatin (N=50) and those with 10 mg of atorvastatin (N=338), the estimated minimum detectable effect size corresponds to a 91.3% reduction in eCD in the former cohort vs. the latter.

Rationale for Sample Sizes

As per the power analysis above, the 1000 targeted patient enrollment is reasonable considering the aims of this study. We anticipate approximately 350 patients will be scheduled for CEA per year from the six participating institutions (Columbia-Presbyterian, St. Luke's Roosevelt, Cornell University, Valley Hospital, Montefiore Medical Center, and Buffalo Medical Center). Approximately 80% are anticipated to be asymptomatic, leaving 280 per year.

Expecting an approximate 75% recruitment rate, 210 eligible asymptomatic patients will be enrolled each year from the six sites. Over five years, this rate allows for 1000±50 patients to be enrolled. Based on our previous R01 grant, we estimate that a) 225 patients will already be on a pre-existing maximal statin regimen of simvastatin, atorvastatin, or rosuvastatin, b) 675 patients will be on a sub-maximal statin regimen of simvastatin, atorvastatin, or rosuvastatin, and c) 100 patients will be on no pre-existing statin regimen.

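### Section 9.3 gives the cumulative alpha, 0.05, as the final critical value in Arm 2; after 0.0116 at the interim the final nominal level should be about 0.0464.

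*Combined protocol and SAP*

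**What the plan says.** **Looks and spending.** Section 9.3 states: "One interim analysis and one final analysis are planned for ARM 2 of the trial, for a total of 2 analyses." The timing is given as "These analyses will be performed when 0.66 and 1.0 fraction of the total number of participants in ARM 2" have completed the assessment at about 30 days. On size, "ARM 2 will have a maximum sample size of 675 participants, we will have approximately 446 participants accrued." The method is "We will use the Lan-DeMets approach, implementing an O'Brien-Fleming-type spending function that allots most of the type I error to the final look." The decision values follow: "The resulting alpha critical values to be used for each analysis are 0.0116 at the interim analysis, 0.05 at the final analysis." Section 9.2 gives the design level, "with power=0.8, $\alpha=0.05$, and expected rates of eCD." Neither section states whether tests are one- or two-sided.

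**Endpoints.** The sections do not agree on the status of dCD.

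- Section 1.1 names both eCD and dCD in every primary objective.
- Sections 9.1 and 9.4 define the primary outcome from scores at both postoperative times.
- Section 9.3 says of an outcome that lists both eCD and dCD that it "is the basis for formal interim analysis plan that follows."
- Section 9.2 makes eCD the response variable of the primary analysis for all aims and adds: "A separate independent analysis for dCD will also be performed."
- Section 9.5 repeats eCD as the primary response and derives the primary outcome from Day 1 only.

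No section gives an alpha level for dCD, a split, a testing order, or a rule for what counts as success.

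**The concern.** A spending function divides one total alpha over the looks. Once some has been spent at the interim, the final test must be stricter than the total. Here the final value equals the total, as if the interim look had cost nothing. The wording presents 0.05 as the value to use, and no other final boundary is given. An analyst who follows the text would declare a final p of 0.048 significant, although the plan's own spending function says it is not. This is the confirmatory threshold for the main randomised comparison of a Phase 3 trial.

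The silence on dCD matters for a related reason. One pair of critical values is attached to an outcome with two components, so the plan does not show what the 0.05 protects.

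**Working it through.** **Inputs.** Total alpha is 0.05 (Section 9.2). Section 9.3 gives the O'Brien-Fleming-type spending, the information fractions t = 0.66 and 1.0, and the stated values 0.0116 and 0.05. The stated interim size agrees: 0.66 × 675 = 445.5, or about 446. Two-sided testing is assumed.

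**Step 1: reproduce the interim value.** The two-sided form, with 0.025 spent in each tail, is

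α(t) = 4 × [1 − Φ(z₀.₉₈₇₅ / √t)].

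At t = 0.66: 2.2414 / 0.8124 = 2.7590; 1 − Φ(2.7590) = 0.002899; × 4 = 0.0116. The plan's interim figure reproduces.

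Alternatives do not reproduce it. Spending 0.05 as 2 × [1 − Φ(1.96/√t)] gives 0.0158, a one-sided 0.025 gives 0.0058, and the classic O'Brien-Fleming boundary gives 0.0137 (with 0.0453 at the final look).

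**Step 2: identify the 0.05.** At t = 1 the same formula gives 4 × 0.0125 = 0.05. This is the cumulative alpha by the final look. The stated pair is therefore the cumulative spend at the two looks. At the first look, cumulative spend and nominal level coincide; at the second they do not.

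**Step 3: error of the rule as written.** The interim cut-off is |Z₁| ≥ 2.524 (p = 0.0116) and the final cut-off is |Z₂| ≥ 1.960 (p = 0.05). Under the null, corr(Z₁, Z₂) = √0.66 = 0.812. Numerical integration gives

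P(|Z₁| ≥ 2.524 or |Z₂| ≥ 1.960) = 0.0534.

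The excess is 0.0534 − 0.05 = 0.0034. With the interim value held at 0.0116, the result stays between 0.0532 and 0.0534 for t from 0.66 to 0.67.

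**Step 4: the final level that holds 0.05.** Solving P(|Z₁| ≥ 2.524 or |Z₂| ≥ c) = 0.05 gives c = 1.992, a nominal two-sided p of 0.0464.

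**Step 5: power cost.** Take an effect with 80% power in a fixed-sample two-sided 0.05 test (drift 1.960 + 0.842 = 2.802). Power over both looks is 80.4% with the final value at 0.05 and 79.5% with it at 0.0464, a loss of about 1 point.

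**Step 6: two endpoints, conditional.** Suppose, as the plan does not say, that eCD and dCD are both tested at these values and either one counts as success. The correlation between the two test statistics is not in the documents, so it is varied (simulation of 4 million trials; the value at 0 agrees with 1 − (1 − 0.0534)² = 0.104).

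| Assumed correlation | Final value 0.05 | Final value 0.0464 |
|---|---|---|
| 0 | 10.4% | 9.8% |
| 0.5 | 9.7% | 9.1% |
| 0.7 | 8.9% | 8.4% |
| 0.9 | 7.5% | 7.1% |
| 1.0 | 5.3% | 5.0% |

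Under that rule, correcting the final value alone would not bring the Arm 2 error back to 0.05 unless the endpoints were perfectly correlated.

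**The case against.** **The 0.05 is a labelling slip.** The pair matches cumulative spend exactly and the function is named, so an analyst who runs it in software would obtain 0.0464 and keep one endpoint at 0.05. That is probably what was meant, and the literal excess is only 0.34 percentage points. It affects only a final p between 0.0464 and 0.05. Both points stand and limit the size of the problem. They do not remove it, because the sentence states what is to be used at each analysis and nothing elsewhere corrects it.

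**The 0.0534 counts every interim crossing as a success.** Section 9.3 leaves continuation to the monitoring board and the funder, who weigh several factors. The realised rate could therefore be lower. But early evidence of efficacy is a stated purpose of the look and alpha is assigned to it, so the stated rule should hold its level when followed.

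**A stronger reading on endpoints.** A reader might infer that eCD and dCD each carry the full 0.05 and that the error is roughly doubled. The documents do not establish this. Sections 9.2 and 9.5 name eCD as the response of the primary analysis, and the detectable effects in Section 9.2 are all for eCD. No section states an either-endpoint rule. The figure near 10% also needs nearly independent endpoints, which is unlikely for the same battery in the same patients. What remains is that the status and alpha of dCD are unstated and the sections conflict.

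**Conclusion.** The final critical value in Section 9.3 is wrong as written. For one endpoint, under two-sided testing at information fractions 0.66 and 1.0, the overall type I error is 0.0534 against a design level of 0.05. The matching final nominal level is 0.0464 (|Z| ≥ 1.992). The numerical effect is small, but the sentence sets a confirmatory decision threshold and should be corrected.

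The dCD issue is secondary and conditional. An Arm 2 error of about 7.5% to 10.4% arises only if either endpoint may support a claim at the stated values and the correlation lies between 0.9 and 0. Both are assumptions. If eCD is the sole primary endpoint, dCD adds nothing to the primary error. A reader might also extend the point to the other primary objectives. The interim plan covers Arm 2 only, and nothing calculated here bears on their status.

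**What to change.** 1. In Section 9.3, replace the final value of 0.05 with a nominal two-sided 0.0464 (|Z| ≥ 1.992), to be recomputed from the information fraction actually reached at the interim. State that testing is two-sided. If the existing pair is kept for reference, label it as cumulative alpha spent.
2. Make Sections 1.1, 9.1 to 9.5 agree on the status of dCD. As Section 9.2 already makes eCD the primary response, the simplest rule is to apply the boundary to eCD in the Arm 2 randomised comparison and to test dCD, with the same spending function, only if eCD is significant. An equal split of 0.025 each would also control the error, at the stricter levels of 0.0042 (interim) and 0.0237 (final) per endpoint.

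The cost is protocol and SAP wording, with no added patients. The corrected final value costs about 1 point of power for eCD. Under the ordered rule, dCD has no confirmatory test if eCD fails. Both changes should be settled before any unblinded Arm 2 comparison is seen, since an order chosen afterwards would not be credible.

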9.4 Outcomes

We have defined our primary outcome on Z-scores based on the mean and standard deviation of cognitive testing change in scores of a surgical reference group before and after surgery (12-25h and 30 days postop/ Day of PO clinical visit).

The cognitive testing has been divided by cognitive domains and the patients are considered to have postoperative early cognitive dysfunction (eCD) based on two criteria to account for both focal and global/hemispheric deficits. Consequently anyone with:

- (a) $\geq 2SD$ worse than reference group in two or more cognitive domains or
- (b) $\geq 1.5SD$ worse than the reference group in all cognitive domains tested will be considered a primary outcome.

If the subjects experience stroke or TIA peri-operatively, they will be considered as having reached a secondary OUTCOME in the study.

9.5 Data Analyses

For all analyses, the primary outcome will be derived from changes in test scores between the day before or morning of surgery (baseline) and the final time point Day 1 post CEA (12-25h post-op). The intention to treat principle will be used for all analyses. All of the analyses will be performed in two general ways. 1) Significant neurocognitive change for both CEA will be defined compared to an appropriate reference group frequency matched for age and type of anesthetic or sedation. Significant eCD will be defined as performance: (1) 2SD worse performance in two or more cognitive domains or (2) 1.5SD worse performance in all cognitive domains.

The following data will be kept for patients having CEA: demographic and risk factor variables (age, gender, race, a history of hypertension, diabetes, level of glycosylated hemoglobin, previous myocardial infarction, and previous CEA), degree of carotid stenosis, all additional cerebrovascular workup (i.e. Intracranial MRA, SPECT scanning, angiography, etc.), laboratory values, all standing medication names, doses, and durations, and all neurologic and neuropsychological scores. In general, for the continuous variables, a two-sample Student's t-test will be used for comparing means between the two groups, patients with eCD and those without eCD. Non-normally distributed variables will be transformed to improve distributional characteristics. In particular, neuropsychometric test scores will be subjected to a square root transform that yields values that are approximately normally distributed and provide analytic results using parametric tests that are similar to those obtained by non-parametric analysis of the untransformed values. Non-parametric techniques will be used for any variables for which suitable transformations cannot be found. Dichotomous variables will be analyzed using a 2 test. Multiple linear and logistic regression models will be used to adjust for the risk factors that are out of balance ($p < 0.10$)

between groups. Logistic regression analysis will be used to determine whether any demographic or risk factors other than CEA significantly affects outcome. Post-operative pain >4 adversely affects performance, for this reason, change scores for each test will be obtained using the patients in the reference group. The cutoff value for pain scores is 4. When data are missing completely at random (MCAR), i.e. when the probability that an outcome is missing does not depend on any outcomes, statistical inference based on completely observed data is valid. If data are missing at random (MAR), i.e. when the probability that an outcome is missing depends on the observed outcomes (such as observed outcome at baseline), inference based on complete data is not valid. All of the aims will use logistic regression with presence of eCD as the response variable as the primary statistical analysis. No patients will be enrolled for reference group study. We have previously collected data for the reference group. Z-scores in the past have been generated based on this surgical reference group's performance to account for practice effect, trauma of surgery, general anesthesia, and the overnight hospital stay experience. The surgical reference group was composed of age- and sex-matched patients 60 years of age undergoing lumbar level laminectomy or microdiscectomy on 2 levels without fusion, no tumor/cyst, or blood loss necessitating transfusion. These patients experience similar surgical and anesthetic times as well as a similar general anesthetic. The mean difference score of the surgical reference group has typically been subtracted from the difference score for the CEA patient and then divided by the standard deviation (SD) of the surgical reference group ($[(\text{Difference CEA} - \text{Mean Difference Reference})/\text{SD Reference}]$) to generate Z-scores.

10 DATA COLLECTION AND QUALITY ASSURANCE

10.1 Data Collection Forms (eCRFs)

The Central Coordinating Committee has created the study worksheets that have been transformed into electronic case report forms (eCRFs) based on the current objectives and hypothesis described in this protocol. The eCRFs must be printed from the study database and submitted for individual site IRB approval.

The data sources collected for the eCRFs (including study worksheets) must be kept secure in individual subject binders, reviewed and signed by site Principal Investigator, entered into the study database(eCRFs), scanned/uploaded to the study database, (see 10.2 Data Management) and made available for study monitoring by the Sponsor and/or corresponding regulatory agencies.

10.2 Data Management

All patient information will be coded. Coding involves the replacement of direct patient identifier from data sets with a linking code by which the data remain identifiable. For linking purposes, we use study specific codes, rather than medical record numbers, social security numbers, or other easily decoded combinations of initials and birth dates. Access to the linking files will be restricted to authorized study personnel and regulatory agencies.

The data will be collected and stored on an encrypted, password-protected multi-user system created and maintained by the Statistical Analysis Center (SAC) at the Mailman School of Public Health at Columbia University. The data management infrastructure created for the trial, and will be responsible for creating

the database where to store and upload the eCRF data and for reporting results to the Data & Safety Monitoring Board (DSMB). All subject research data will be coded with subject ID number. All laboratory and clinical information obtained from this research will be maintained in locked offices and will be accessible only to the main investigators of this project. The electronic database used during the trial is secure and password protected. This web-based system, developed at the SAC, ensures confidentiality and data integrity through the use of a secure server; password protected access, and encrypted data. Specifically, the browser-based front end of the system uses 128 bit Secure Sockets Layer (SSL) technology to ensure that users are properly authenticated to the server and all data exchange occurs in an encrypted fashion. High level of security will be actively maintained. Subjects' information will not be discussed in any form in the presence of other subjects or non-study personnel. Subjects will only be referred to by their subject unique ID number in all study documents. Specimens will be coded using the subject ID number only. For every research participant, relevant clinical information is documented on electronic case report forms and source documents and stored in the secure electronic database or in a double locked area. All study records will be maintained for 7 years. The unique study ID will be generated by the data management system (via the web interface) when a patient enrolls in the study. PHI will be strictly limited to those items essential to the operation of the trial and the specified analyses (dates of diagnosis, dates of treatment, etc.) Clinicians and other personnel involved with patient recruitment, treatment and follow-up will obviously have access to both patient identifiers and the trial data, including the subject ID. Typically, a subject binder/folder is created for each participant, which contains source documents and other information collected for the trial, including subject ID. It is the responsibility of the clinical team to store these folders in a secure place and ensure that they are available only to authorized personnel. Trial personnel not involved in patient contact, including data staff and statisticians, will not have access to identifying information. All trial data, including the subject ID, will be stored on the SAC's secure database servers. The SAC's data systems have been approved for the collection of clinical research data by CUMC IT Security.

In addition, the data center (SAC) will design the database to evaluate, validate and monitor trial data as part of an ongoing process. The initial validation takes place as early as possible in the data collection process, including real-time validation for range checks, limits on categorical variable entry, checks for completion and consistency, etc. Further error checking, including validation for completeness, is performed when data is posted. Since some errors (in changes over time, and consistency between different forms or scales) cannot be detected on initial data entry, validation checks are performed daily. All data errors and queries are processed promptly. Regular reports to investigators and coordinating centers on accrued data identify unusual or unexpected data points and request that they be confirmed or corrected.

10.3 Quality Assurance

10.3.1 Training

During the site initiation visit (SIV), members of the CCC will train the site's study members on the study protocol and procedures. [name] and/or his representative will also visit each study site, virtually or inperson, weekly for the first 6 months after their site initiation visit (SIV) and then monthly to insure protocol procedures are followed clearly, consistently, and while keeping patient safety forefront. There will also be monthly conference calls with all of the sites to make sure that any concerns or questions are addressed and shared with the whole study team. Further visits will be on an as needed basis if a site

shows a pattern of study violations and/or have procedural errors that show the need to receive booster training or further study monitoring.

In addition, the study team's neuropsychologist, [name] and/or [name], will conduct the initial training for the neuropsychometric measures for study staff that will administer these tests (i.e. coordinators). They will test and certify the study members and additional training will be provided via conference/video calls and on-site visits as needed.

The initial protocol training will be supplemented by teaching moments provided during the Monthly Conference Call with all study sites.

